3.2 Study Endpoints

3.2.1 SAFETY ENDPOINTS

Safety is the primary endpoint and analysis will focus on the following endpoints at each time point from the start of dosing through the 4-week treatment and observation period, and at a 4-week follow-up visit:

- EKG
 - Patients in the Assigned Dosage Groups (1 and 3) will also have an EKG at baseline and within 3 days prior to the their visits as described in [5.1.2](#).
 - In the event any EKG abnormalities appear to result from treatment in the Assigned Dosage Group then additional EKG may be required as described in section [5.5.2](#)
- Before and after the Active Treatment phase
 - Physical exam with vital signs, including orthostatic blood pressure
 - Hematology
 - Serum Chemistry
 - Urinalysis
- Active Visits, weeks 1-4
 - Vital signs findings, including orthostatic blood pressure,
 - Adverse Event (AE) reporting
 - Assessment of concomitant medications

3.2.2 EFFICACY ENDPOINTS

3.2.2.1 Main Efficacy Endpoints

- The primary efficacy endpoint will be the determination of clinical improvement by the Investigator as documented in the Clinical Global Improvement (CGI) scale and subscales (including severity and improvement) based upon his/her clinical observation and the results of the test scores as measured in the overall scores by the tests described below.

3.2.2.2 Additional Efficacy Endpoints

- Changes from baseline in the individual dimensions of the VABS questionnaire
- Changes from baseline in the VABS caregiver rating scale
- Changes from baseline in the ADOS scores and subscores
- Changes in the Clinical Global Impressions scale and subscales.
- Changes in the SAS
- Changes in the SRS
- Changes in the ABC-C scale and subscales
- Clinical opinions of observable changes from baseline.

3.2.3 PHARMACOKINETICS

The pharmacokinetics of L1-79 will be determined in the first week of treatment for the first 5 patients assigned to each Dose Arm (100 mg t.i.d. or 200 mg t.i.d.) The results of these analyses will be used to determine the exposure to L1-79 at the two proposed doses

3.3 Regulatory Compliance

This trial will be conducted in compliance with the study protocol. ICH and Good Clinical Practice (GCP) guidelines and all applicable regulatory requirements will be adhered to by all personnel at all times.

3.4 Principal Investigator and Study Coordinator

It is the responsibility of the Investigator to execute this protocol as written in all details.

The Investigator will appoint a study coordinator with specific responsibilities for assuring that all of the elements of this protocol are conducted exactly as written. The study coordinator's responsibilities will include, but not be limited to:

- Scheduling the patient visits and assuring their timely presence
- Conducting those elements of the protocol assigned to the study staff by the Investigator (e.g., collection of vital signs, blood pressure, VABS II, ABC, caregiver forms, etc.)
- Assurance that all data are entered into the database within 3 days of the receipt of the data,
- Assuring that all data required by the sponsor are delivered to the sponsor in a timely manner.
- Training of study staff on the GCP guidelines and the details of this protocol, the methods and procedures by which this protocol is to be executed, and oversight over the execution of the protocol.

4.0 STUDY POPULATION

The study will enroll 40 subjects who meet the inclusion and exclusion criteria outlined below and who received at least one dose of the study medication.

Only males will be enrolled in this study due to the lack of nonclinical reproductive toxicology. Subjects will be randomized or assigned to each of the treatment groups described herein such that 15 subjects are randomized to each L1-79 treatment arm at either 100 or 200 mg t.i.d., and 10 subjects will be randomized to t.i.d. placebo

4.1 Inclusion Criteria

- Subjects or their care givers willing to sign informed consent or to have informed consent provided by their legal guardians or proxies. ([Appendix B](#)). All subjects <18 years old or those unable to care for themselves must have the caregiver's consent.
- Subjects must be between the ages of 13 and 21 years of age
- Subjects must be male
- Subjects must be willing and able to participate in the testing procedures sufficient to obtain valid scores on the tests used herein.
- Must be stable on no more than one concomitant medication, and no planned changes in psychosocial interventions during the trial
- Subjects in the Assigned Dosage Groups must be tolerant of blood draws and electrocardiograms
- Diagnosis of ASD based upon the DSM-5 criteria and confirmed with the ADI-R and ADOS test that confirms a diagnosis of autism, and expert clinical opinion ([Appendix F](#)).
- Subjects must, in the opinion of the Investigator, be sufficiently tolerant and capable of complying with the requirements of this trial. For example, patients who will not tolerate blood draws or EKG are not qualified candidates for this study.
- Signed study compliance agreement ([Appendix D](#)) by the patient or caregiver
- As the Assigned Dosage Group will have repeated blood draws and EKG the investigator must be satisfied that the first 5 patients assigned to each dosage group are willing and able to comply with this regimen

4.2 Exclusion Criteria

- Sexually active males
- Fragile-X syndrome, Rett syndrome, or other co-morbidity including, but not limited to, cancer, asthma, genetic disease, or any disease or syndrome that requires drug therapy.
- DSM-5 diagnosis of schizophrenia, schizoaffective disorder, alcohol use disorder or ADHD
- Active epilepsy
- Out of range hepatic or renal function tests

- Presence of any active medical problem (e.g., unstable seizure disorder or heart disease)
- Any unexplained laboratory value
- Subjects requiring more than 1 medication for the treatment of autism, or who have not been weaned to their lowest tolerable dose of medication
- Uncontrolled intercurrent illness including, but not limited to, ongoing or active infection, symptomatic cardio-vascular disease, hepatic disease, renal disease, skeleto-muscular disease, HIV, HCVA, HBV, or psychiatric illness/social situations that would limit compliance with study requirements.
- Any disease that requires chronic treatment.
- Any disease that requires treatment with immunosuppressive drugs
- Current or lifetime diagnosis of severe psychiatric disorder (e.g., bipolar disorder, etc.);

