An exploratory study intended to observe the effects of L1-79, when administered to patients with autism spectrum disease, was initiated at two sites in New Jersey. L1-79 was given to 10 patients to date on a t.i.d. schedule. Preliminary results indicated that L1-79 reduced the core deficits in a number of subjects, with the racemic form of the drug being more effective than either of the two stereoisomers alone. Utilizing the Aberrant Behavior Checklist – Community (ABC-C), Autism Diagnostic Observation Scale (ADOS), and Connor Parent Rating Scale (CPRS), improvements in all of the core symptoms of autism have been observed to occur quickly in subjects of both sexes and

ranging in age from 2½ to 24 years of age, with continual improvement with treatment over time.

Most of the clinical experience with L1-79 for the treatment of autism is with doses of 100-300 mg t.i.d.. This study seeks to quantify the safety and efficacy of L1-79 administered t.i.d. in doses of 100 or 200 mg to subjects with a diagnosis of autism based upon their ADOS results in a prospectively randomized and double-blind manner.

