3.0 DESIGN AND METHODS

3.1 Study Design

This is a five-arm design that incorporates 2 open label groups whose doses are known for the purpose of understanding PK/PD and to determine if there are any EKG changes associated with the administration of L1-79, and a 3-group prospectively randomized, double-blind, trial of L1-79 at 2 dosage levels versus placebo.

Two dosages of L1-79 will be tested in this study: 100 mg t.i.d. and 200 mg t.i.d. The investigators in this study have the most experience with these two dosages during exploratory use of L1-79 described above. In preliminary observations in a number of patients between the ages of 2.75 and 24 years of age doses between 90 to 400 mg t.i.d. were well tolerated, and no evidence was found that suggests a need for weight based dosing. These findings were presented to the FDA.

The first cohort of 20 patients to be enrolled will all receive L1-79 100 mg t.i.d., and will be comprised of 3 groups of patients. The first 100 mg group will differ from the others in that they will get blood samples drawn for PK analysis and EKGs will be taken. The safety and PK data from this group will be submitted for FDA review and acceptance before the 200 mg t.i.d. cohort will be enrolled. The remaining 15 patients in this cohort will be randomized to receive either L1-79 100 mg t.i.d. or placebo on a 2:1 basis (2 L1-79 patients for each placebo patient). While the FDA is reviewing the data from the first 5 patients all 100 mg t.i.d. patients will continue to be treated.

The second cohort is identical to the first. The initial 5 patients to be enrolled will differ from the others in that they will get blood samples drawn for PK analysis and EKGs will be taken. The safety and PK data from this group will be submitted for FDA review and acceptance. The remaining 15 patients in this cohort will be randomized to receive either L1-79 200 mg t.i.d. or placebo on a 2:1 basis (2 L1-79 patients for each placebo patient). While the FDA is reviewing the data from the first 5 patients all enrolled patients will continue to be treated

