5.5.1.7 Concomitant Medications

As documented in the history and at the screening visit, no patient currently receiving polytherapy for autism will be enrolled in this trial. Any agent which is being prescribed for the treatment of ASD will be noted as such in the eCRF. Subjects identified for accrual into this trial will be weaned to the lowest dose of any prescribed psychotropic medication over the two to four weeks preceding their screening visit deemed effective by the Investigator.

All prescription and nonprescription medication taken by the patient from 14 days prior to screening and up to and including the final visit will be recorded in the medical record and on the eCRF. Any addition, deletion, or change in the dose of these medications must be recorded.

Because the mechanism of L1-79 is the inhibition of catecholamine synthesis, the potential exists for interactions with neurologically active, and other, drugs. Investigators will be diligent in observing potential drug interactions and should appropriately reduce the dose of any concomitant medication that is observed to be potentiated in the presence of L1-79.

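### The entry criteria do not exclude patients already treated with L1-79, so returning tolerators could enter unrecorded, with most effect in the small open-label groups

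*Combined protocol and SAP*

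**What the plan says.** Section 1.0 of the combined protocol and SAP describes an exploratory autism study: "L1-79 was given to 10 patients to date on a t.i.d. schedule". It adds that "Preliminary results indicated that L1-79 reduced the core deficits in a number of subjects" and that improvements "have been observed to occur quickly in subjects of both sexes and" "ranging in age from 2½ to 24 years of age". Section 3.1 states that "The investigators in this study have the most experience with these two dosages during exploratory use of L1-79 described above" and that "doses between 90 to 400 mg t.i.d. were well tolerated".

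Sections 4.1 and 4.2 restrict entry to males aged 13 to 21 with at most one stable concomitant medication. The criterion closest to this point excludes "Subjects requiring more than 1 medication for the treatment of autism, or who have not been weaned to their lowest tolerable dose of medication". No criterion there or in the Synopsis names previous L1-79 treatment. Section 6 plans no subgroup or sensitivity analysis by earlier exposure.

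On data capture, Section 5.5.1.7 requires recording of "All prescription and nonprescription medication taken by the patient from 14 days prior to screening and up to and including the final visit". Section 5.12 starts at screening instead. The medical history in Section 5.5.1.1 has no time limit but does not ask about L1-79. Appendix A lists a form for prior and concomitant medication without giving a look-back period.

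**The concern.** A male aged 13 to 21 who took L1-79 in the exploratory study and has since stopped passes every listed criterion, provided he meets the general ones. If he comes back because he tolerated the drug or improved on it, he is selected on the outcomes this trial measures. Safety is the primary endpoint, and such patients are likely to have fewer adverse events than naive patients.

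Groups 1 and 3 are the exposed part of the design. They have 5 patients each, are open label and are filled by assignment, so nothing in the allocation offsets the selection. Under Sections 4.3, 5.1.1 and 5.9.3.3, the first-week safety, PK and EKG data from Group 1 go to the FDA before the 200 mg cohort can start. Because recording of earlier use is not required, the report could not reliably separate returners from naive patients.

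**Working it through.** The plan gives no figure for returning patients and no adverse event rate, so there is no planned value to reproduce. The group sizes do add up: 5 + 10 + 5 + 10 + 10 = 40.

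**How many could return.** Section 1.0 gives 10 treated patients with ages running from 2½ to 24. The youngest and the oldest both fall outside 13 to 21, so at most 10 − 2 = 8 could be eligible. At least one patient was female, but she may be one of those two, so the sex limit does not lower the cap with certainty. The documents do not give the number of males aged 13 to 21; the possible range is 0 to 8. This takes the stated count and age range as describing the same patients, and the count is as of the time of writing.

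**Chance of seeing an event in Group 1 (n = 5).** Let p be the event probability in a naive patient, with patients independent. The documents give no p; 20% is assumed, with a range of 10% to 30%. Two returners leave 3 naive patients.

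- No returners: 1 − (1 − p)^5
- Two returners at zero risk (extreme case): 1 − (1 − p)^3
- Two returners at half the naive risk: 1 − (1 − p)^3 × (1 − p/2)^2

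| Assumed p | No returners | Two, zero risk | Two, half risk |
|---|---|---|---|
| 10% | 41% | 27% | 34% |
| 20% | 67% | 49% | 59% |
| 30% | 83% | 66% | 75% |

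For p = 20%: 1 − 0.8^5 = 0.672; 1 − 0.8^3 = 0.488; 1 − 0.512 × 0.81 = 0.585.

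**Ceiling for the whole active sample.** There are 5 + 10 + 5 + 10 = 30 active patients. If all 8 possible returners were on active drug at zero risk, a true 20% rate would appear as 0.20 × 22/30 = 14.7% (10% as 7.3%, 30% as 22%). This needs every assumption at its extreme and is an upper bound on the distortion, not an expected value.

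**The case against.** The strongest reply is that no text says any exploratory patient will be enrolled, so the effect may be nil. That stands, and it limits the point to an open route for bias. The zero-risk assumption is also extreme: having tolerated a drug once does not remove the risk of, for example, sedation. The half-risk column shows how much smaller the fall becomes.

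The escalation decision is wider than an event count, since it also rests on PK, EKG and FDA review, and Section 3.1 says the exploratory findings were presented to the FDA. Data capture is not precluded either: an investigator could note earlier L1-79 use in the history or on the Appendix A form. Both replies are fair, but neither makes the exposure visible by design.

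Three stronger readings are tempting and are not supported:

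- A reader might infer that a patient who finished the 100 mg cohort could enter the 200 mg cohort. Section 4.3 calls for 20 additional patients and the Synopsis and Section 4.0 count 40 subjects, which speaks against re-entry.
- A reader might infer a systematic CGI bias in favour of the drug. Groups 2, 4 and 5 are randomised 2:1 within each dose level, so earlier exposure is balanced across arms in expectation. What remains is enrichment and possible recognition of the drug by patient, caregiver or CGI rater. Even the direction is uncertain, because residual benefit at baseline could leave less room to improve.
- A reader might infer from Section 4.1 that Groups 1 and 3 are chosen for tolerance of L1-79. The criterion there concerns blood draws and EKG.

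**Conclusion.** The gap is real: previous L1-79 exposure is neither excluded nor required to be recorded, although patients treated by investigators of this trial exist and some may meet the age and sex limits. The number is unknown, between 0 and 8. The consequence is most direct in open-label Groups 1 and 3, above all Group 1. With two returners of five, the chance of seeing at least one event there would drop from 67% to 49% at an assumed 20% rate and zero risk in returners, and only to 59% if their risk were halved. All event rates are assumptions, not document figures. In the randomised groups the issue is how far results apply to naive patients and how secure the blind is, not an expected imbalance between arms. This is a cheap improvement worth making, not a defect that undermines the trial. Most of the consent form is absent from the documents, so a statement there cannot be ruled out, but Section 4 sets out who may enter.

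**What to change.** Add to Section 4.2 and the Synopsis an exclusion for any previous exposure to L1-79 (racemic AMPT) or to either isomer; Section 1.0 compares the racemate with the separate isomers, so both belong in the wording. Add a question on this to the Section 5.5.1.1 history with no time limit. State that the placebo rollover in Section 5.1.4 is unaffected. If any such patient is already enrolled, flag him in the database and show the safety and CGI tables with and without him.

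The cost is an amendment with one criterion and one history question, and the loss of at most 8 candidates from the recruitment pool. The sample size stays at 40. If the sponsor prefers not to exclude these patients, recording and flagging them would address the analysis problem but not the selection into Groups 1 and 3.

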4.3 Group Sizes

The study includes a total of 40 patients equally allocated to 2 placebo controlled treatment arms (100 mg or 200 mg L1-79 t.i.d. The first 5 patients in each Treatment Arm enrolled and will be required to provide EKG tracings and blood specimen(s) for determination of pharmacokinetics for the estimation of exposure. Once this lead-in group has completed one-week of treatment and EKG tracings are not abnormal and blood specimen(s) for the determination of L1-79 concentrations have been analyzed, and a report on the PK and safety data from this group has been reviewed by the FDA and permission from the FDA is obtained to escalate the dose, then, 20 additional patients will be enrolled and treated in the same manner as the 100 mg t.i.d. group, such that 5 open label patients will be treated as described above and 15 patients will be randomized 2:1 to receive 200 mg L1-79 t.i.d.

5.0 STUDY PROCEDURES

5.1 Consent and Assignment of Subjects to Treatment

Each patient or their representative must sign a copy of the informed consent document. The patient will be asked to provide assent to participate in the study ([Appendix B](#)). The study staff will explain this form in non-technical language, in detail, and will answer all questions that a patient might ask. Staff will explain to all subjects that subjects who qualify for entry into this trial will receive an experimental treatment which they must take daily as instructed and must come back to the clinic for regularly scheduled visits.

The patient, or caregiver of each patient will sign the Study Compliance Agreement ([Appendix D](#)) in which they agree to administer the test medication as instructed by their attending physician in compliance with this protocol. Further, this agreement stipulates that the caregiver of each patient will complete their obligations under this protocol as instructed by the Investigator and his/her staff; including visit attendance, test form completion, reporting of adverse events, and so forth. Additionally, this agreement requests, but does not require, that caregivers provide any *ad hoc* comments regarding the behavior of the patient or their responses to treatment be forwarded weekly to the Investigator to document changes in the patient's condition at home and to add any notes to the database that are appropriate to understanding the response of the patient to treatment.

After satisfying entry criteria and giving signed informed consent and agree to the compliance document, subjects will be enrolled in the trial

5.1.1 ASSIGNMENT OF PATIENTS TO GROUPS

At each of the two tested dosage levels, the first 5 patients in each group will be assigned to receive the specified dose of either 100 mg t.i.d. or 200 mg t.i.d., whereas the following 15 patients in that group will be randomized to receive the specified dosage or placebo. After being assigned to a treatment arm each patient will be assigned a study number comprised of a 2-digit site identifier and a 3-digit patient identifier.

No patient will receive more than 100 mg t.i.d until permission to escalate to 200 mg t.i.d. is obtained from the FDA after their review of the first week of safety and PK data from the 100 mg group. This permission will follow if the safety data submitted for the first week of dosing in the Assigned Dosage Group is assessed by the FDA to be sufficiently safe to allow for a dosage escalation.

Each study site will be identified by a 2-digit number beginning with 01. Each patient screened for admission into the study will be assigned a unique sequential number that also identifies their study site. Thus, the 1st patient enrolled in the first study site will be patient 01-001 and the 2nd patient enrolled at the 2nd study site will be patient 02-002.

Study numbers will not be assigned until a patient is qualified and entered into the trial. Screening failures will not be assigned numbers. However, a list of screen failures and their demographic data will be maintained by the Investigator.

Patients will be enrolled and receive their first dose within 3 weeks of completing the screening procedure.

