APPENDIX E: SAMPLE COLLECTION METHODS.....		58
APPENDIX F: DSM-5 DIAGNOSTIC CRITERIA FOR AUTISM SPECTRUM DISORDER		59

RESTRICTED DISTRIBUTION OF PROTOCOLS

- This protocol contains information that is confidential and proprietary. The information contained herein is provided for the purpose of conducting a clinical trial in collaboration with [name].
-
- The contents of this protocol may be disclosed to study personnel under your supervision and to your Institutional Review Board(s). The contents of this protocol may not be disclosed to any other parties (unless such disclosure is requested by [name]).

PROTOCOL SYNOPSIS

- Study Drug: L1-79
- Protocol Number: HT 02-121

Protocol Title: A Phase 2 Safety Study of L1-79 in the Treatment of Autism

- Study Phase: 2
- **Study Design:** This study has a dose escalating cohort design. Treatment arms consist of L1-79 at doses of 100 mg t.i.d (or placebo), or 200 mg t.i.d., (or placebo). Pharmacokinetics will be assessed in initial cohorts of 5 patients for each dose group followed by a double blinded, placebo-controlled assessment of PK/PD and safety in a cohort of 15 patients randomized 2:1 active to placebo. Groups 1& 2 below can start simultaneously. While the FDA is reviewing the data from Group 1, Groups 2 and the placebo patients randomized with Group 2 will be ongoing. All 5 subjects assigned to Group 1 (100 mg L1-79) must have completed the PK portion of the study with results analyzed and accepted by the FDA before subjects in Groups 3-5 can begin treatment.
- Sample Size: N=40
 - Group 1 (n=5) 100 mg L1-79 (1x100mg capsule+1 placebo capsule)
 - Group 2 (n=10) 100mg L1-79 (1x100mg capsule+1 placebo capsule)
 - Group 3 (n=5) 200 mg L1-79 (2x100 mg capsules)
 - Group 4 (n=10) 200 mg L1-79 (2x100 mg capsules)
 - Group 5 (n=10) Placebo (2 placebo capsules)

All Groups will receive the assigned study drug three-times daily.

- **Study Population:** Male subjects with autism between the ages of 13 and 21 years of age who meet the entry criteria and who are able to complete standardized measures allowing them to participate in this study.

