- **Major Inclusion Criteria:** Males between 13 and 21 years of age, signed informed consent, normal clinical laboratory values, DSM-5 compliant diagnosis of autism spectrum disorder, confirmed by the Autistic Diagnosis Interview Review (ADIR), and by the Autism Diagnosis Observation Schedule (ADOS) score consistent with a diagnosis of autism, no more than one concomitant medication, on a stable regimen for at least 2 weeks prior to enrollment and no planned changes in psychosocial interventions during the trial.

- **Major Exclusion Criteria:** Any co-morbidities, including Fragile-X syndrome, epilepsy, Retts syndrome, ADHD, or other disease or syndrome aside from autism that requires treatment. Any other psychiatric disorder, or out of range lab values. DSM-5 diagnosis of schizophrenia, schizoaffective disorder, alcohol use disorder; active medical problems: unstable seizures (>2 in past month), significant physical illness.
- **Experimental Treatment:** L1-79 at doses of 100, or 200 mg, or placebo 3 times daily for 4 weeks.
- **Non-Experimental Treatment:** Placebo.
- **Dosage and Administration:** L1-79 or placebo, as assigned or as randomized, will be administered orally according to the regimen above.
- **Evaluation Schedule:** Subjects will be evaluated within one week prior to study accession, and weekly throughout the dosing period, and again 4 weeks after the cessation of treatment. The Assigned Dosage Groups (Groups 1 and 3) will have PK blood draws and EKG the randomized group will not have.
- **Safety Measures:** All Groups will have regularly scheduled complete history and physical examination that includes orthostatic blood pressure measurements, vital signs, CBC, differential, platelet counts, urine analysis, serum analytes including: total protein, albumin, glucose, BUN, creatinine, direct and total bilirubin, alkaline phosphatase, phosphorous, calcium, AST, ALT, sodium, potassium, chloride, bicarbonate, T₄, TSH, and adverse events assessments. The Assigned Groups (1 and 3) will also have electrocardiograms taken at the study screening visit and at the week 1.
- **Total Study Duration:** It is expected that the entire study from screening of the first patient until the last patient enrolled has completed the last visit to require a total of 36 weeks. This period was estimated to include an 8 weeks recruitment, 8 weeks for screening, and 8 weeks' for treatment of all patients enrolled in the study and 8 weeks for follow-up.

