5.1.2 ASSIGNED DOSAGE GROUPS

The first 5 patients in each dosage group will be assigned to receive the active medication in an open label fashion. These groups will be treated identically to the Randomized group with 4 exceptions:

- Patients in this group will have blood samples drawn at baseline before and 1h after dosing, and at each active treatment visit 1h after dosing to determine their blood levels of L1-79 for pharmacokinetic and pharmacodynamics analysis.
- Patients in this group will have EKG taken at baseline and within 3 days prior to the Week 1, 2, 3, and 4 treatment interval visits as well as at the 1 week and 4 week post dosing follow-up visits. Patients in this group will have vital signs, physical exam, and ASD assessments will be performed, including: ABC, SRS, RBS-R, CGI-S, and CGI-I be assessed at 1-week post-dosing. Patients in this group will have blood and urine samples drawn at baseline at baseline before dosing, at week 1, 2, and 3 active treatment visit 1h after dosing, and at the 1 week post dosing follow up for safety analysis.

Following the Week 1 visit for these patients and the completion of all assays for samples taken at the Week 1 visit, a report will be submitted to the FDA on the results from these patients. A second report on the results of these patients will be sent to the FDA following the final 1-week post-dosing visit for this group of patients.

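### The Week 1 report that opens the 200 mg cohort covers only the five open-label 100 mg patients, and need not show non-serious AEs or orthostatic readings from randomised patients already dosed

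*Combined protocol and SAP*

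**What the plan says.** **What the gate looks at.** Section 4.3 sets the condition on the first five patients: "Once this lead-in group has completed one-week of treatment and EKG tracings are not abnormal", with drug concentrations analysed and a report on that group reviewed by the FDA. Section 5.1.2 says that after their Week 1 visit and assays "a report will be submitted to the FDA on the results from these patients". Sections 3.1 and 5.9.3.3 describe the same report. Section 5.1.1 once speaks more loosely of the 100 mg group, but its next sentence narrows this to the "safety data submitted for the first week of dosing in the Assigned Dosage Group". The second report in 5.1.2 covers the same five patients.

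**Who else may be on drug.** The Synopsis states "Groups 1& 2 below can start simultaneously", Group 2 being the ten randomised to 100 mg. Section 5.1.1 puts randomisation later ("the following 15 patients in that group will be randomized to receive the specified dosage or placebo"). Section 5.1.3 places it after the five are enrolled, not after their report. Section 3.1 adds: "While the FDA is reviewing the data from the first 5 patients all 100 mg t.i.d. patients will continue to be treated".

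**What is collected and where it goes.** Randomised patients have orthostatic blood pressure and AE questioning at the weekly visits (5.5.1.3, 5.5.1.4, 5.9.2), entered within 3 days (8.2). Section 8.1.1 sends non-serious AEs to the FDA in the IND annual report. No FDA route is given for orthostatic readings.

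**The concern.** Safety is the primary endpoint and this is the trial's only dose escalation. Section 5.2.3.1 singles out dystonia, extrapyramidal signs and cardiovascular events for attention. Questioning and blood pressure measurement can reveal these without PK sampling or an EKG, so randomised patients at the same dose can supply relevant evidence. A cluster of mild orthostatic drops or early extrapyramidal signs in Group 2 could be in the database and absent from the report, with the protocol followed to the letter. Section 5.14 treats grade 1 and 2 events as reason to pause a patient's dosing, yet the plan does not require them to be shown when the dose is doubled for the next cohort.

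**Working it through.** The plan states no figure to reproduce: section 6.1 says the study is descriptive and lacks power. The check has two parts.

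**1. Does any rule carry the data into the report?**
- Sections 3.1, 4.3, 5.1.1, 5.1.2 and 5.9.3.3 all confine it to the five.
- Section 8.1 sends serious events to the sponsor and monitor within 24 hours and to the IRB.
- Sections 5.13 and 5.14 discontinue a patient with a grade 3/4 event and stop a site after two.
- Section 5.5.2 provides an EKG as needed for a possible cardiovascular event.
- The DMC appears only in 5.14, for restarting medication after a grade 3/4 event.

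None of these puts non-serious AEs or orthostatic readings from randomised patients into the Week 1 report.

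**2. What could the extra patients add?** For one specified event type not seen in n active patients, the exact one-sided 95% upper limit on incidence is 1 − 0.05^(1/n):

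| Active patients n | Limit |
|---|---|
| 5 (Group 1 alone) | 45% |
| 7 (2 more) | 35% |
| 8 (3 more) | 31% |
| 10 (5 more) | 26% |
| 12 (7 more) | 22% |
| 15 (all of Group 2) | 18% |

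Which row applies depends on accrual and assay time, and the plan gives neither accrual by cohort nor assay time. Suppose randomised patients follow the five, as 5.1.1 and 5.1.3 say. Count from the last Group 1 first dose. The Week 1 assays are complete at 1 + A weeks, where A is the assay time. Patients with a full week by then were dosed by week A, so they number r × A at r patients per week. Two-thirds are expected to be active.

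Assume A = 0 to 2. For r, the Synopsis says of the total duration "This period was estimated to include an 8 weeks recruitment". Spreading the 20 patients of the 100 mg cohort over 8 weeks gives r = 20/8 = 2.5, an assumption:

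| A (weeks) | Randomised, full week (2.5A) | Expected active (× 2/3) | n, about | Limit | Randomised, any dose: 2.5(1 + A) |
|---|---|---|---|---|---|
| 0 | 0 | 0 | 5 | 45% | 2.5 |
| 1 | 2.5 | 1.7 | 7 | 35% | 5 |
| 2 | 5 | 3.3 | 8 | 31% | 7.5 |

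- At r = 1, at most 2 randomised patients (1.3 active) have a full week. Then n is about 6 and the limit 39%.
- At r = 40/8 = 5 and A = 2, 10 randomised (6.7 active) give 22%. That rate counts 200 mg patients, who cannot enrol before the gate, so it is generous.
- If the groups start together and accrue equally (also an assumption), 5 randomised patients are added at each A. With A = 0 that is 3.3 active, n about 8, and 31%.
- The 18% limit needs all 15 randomised patients, hence all ten active ones, to have a full week by the cut-off.

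**The case against.** The five are the only patients with known dose, PK samples, scheduled EKGs and weekly laboratory tests. The FDA asked for their one-week follow-up (5.9.3.3), decides on escalation and can ask for more. It has also been shown exploratory experience in which "doses between 90 to 400 mg t.i.d. were well tolerated" (3.1). The top dose is put at 300 mg of Demser daily, 15% of 2 g/d (5.3). The 200 mg cohort has its own five-patient lead-in. Every patient is observed for at least 2 hours after the first dose, and 5.14 pauses dosing for grade 1 or 2 events, although 5.13 leaves this to discretion for grade 2. If 5.1.1 and 5.1.3 govern the order, few or no randomised patients may have a full week of data. All of this stands and limits the consequence. None of it places the data before the reviewer.

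The statistical objection also has force. The zero-event limit suits a specific event, not AEs overall: at an assumed 20% one-week rate of any AE, 15 patients show none with probability 0.8^15 = 3.5%, and five with probability 0.8^5 = 33%. Once an event appears, a blinded listing cannot say whether drug caused it.

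A reader might infer that serious events in randomised patients go unnoticed at escalation, or that the plan bars their data from the report. Neither follows. The 24-hour alerts and the grade 3/4 rules cover every patient, and 8.1.1 assigns an annual reporting duty without forbidding earlier submission. The data are not required, which is less than being withheld.

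**Conclusion.** The point holds as a low-end minor one: a cheap improvement to the escalation report, not a flaw that makes the escalation unsafe. On the text, the report is limited to five patients while others in the same cohort may already be dosed.

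The size of the gain is uncertain. The limit stays at 45% if nobody else has been dosed, and is about 35% to 31% with two or three further active patients. That range rests on the assumed accrual of 2.5 per week and assay time of 1 to 2 weeks, and on an expected two-thirds on active drug. It would be tempting to say that the plan gives up a fall from 45% to 18%. The documents do not support this as an expected gain: the 18% requires a full week in all ten Group 2 patients, which the ordering in 5.1.1 and 5.1.3 makes unlikely.

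**What to change.** In 5.1.2, after the sentence on the Week 1 report, and with a cross-reference from 5.1.1, add:

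> The report will append a blinded, pooled listing of AEs, SAEs and vital signs, including orthostatic blood pressure, with days on treatment, for all randomised 100 mg cohort patients dosed by the date the last Group 1 Week 1 assay is completed, using data as entered. The report will not wait for further data or cleaning of this listing.

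The date fixes the cut-off. Days on treatment let the reader separate full-week from part-week exposure.

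The cost is this short addition and one listing from data already being entered, with no new procedure. The code stays closed as 5.1.4 requires. The drawbacks are that about one-third of those listed are on placebo, so events cannot be attributed to drug, and that the data are uncleaned. The listing also lacks PK, scheduled EKGs and on-treatment laboratory results before Week 4, and it may be empty.
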